#### **Lab Visits**

Participants will be asked to avoid cycling or walking to the appointment on the mornings of each trial. They will be encouraged to use motor or public transport, arriving at the laboratory for ~07:30. Upon arriving at the laboratory, participants will be asked to complete a set of validated (Groningen Sleep Scale, International Physical Activity Questionnaire (IPAQ), Hospital Anxiety Depression Scale (IPAQ), SF-12 Health Survey, Diabetes Quality of Life (DQOL)), and non-validated questionnaires (perceived stress) on a computer before laying supine, starting a 60-minute 'steady state' period. This should take approximately 15 minutes. During the following 60 minutes resting blood pressure will be taken using an automatic device, and a superficial femoral artery (SFA) flow mediated dilation (FMD) ultrasound scan will be conducted using the non-invasive procedures described below. A transcranial doppler (TCD) ultrasound will assess cerebral blood velocity (CBv) and a Duplex ultrasound will measure the blood velocity and diameter of the internal carotid artery (ICA). Using a venepuncture, whole blood (3ml) will be sampled from an antecubital vein for the later analysis of baseline endothelin-1 (ET-1) Vascular cellular adhesion molecule (VCAM-1), Intracellular adhesion molecule (ICAM-1) and Interleukin-6 (IL6) concentrations. Blood will be drawn by a trained phlebotomist, and samples stored at -80° until later analysis using the procedures described below. Once this is complete (~09:00), participants will then be supervised while they sit at a workstation in an upright chair, minimising lower body movement.

During this time, food intake will be restricted until lunch (3.5 hrs). However, in the case of a hypoglycaemic episode (blood glucose <4mmol.l), participants will be provided with 15g of carbohydrates (Skittles). Blood glucose will be reassessed after 10-minutes. Should blood glucose still be <4.0 mmol/L, further 15 g of carbohydrates will be provided. The process will be repeated until blood glucose returns above 4 mmol.l.

During the *Sedentary* trial, participants will remain seated for 7-hours at a workstation where they will have access to the internet and will be able to work, read etc., To replicate free-living conditions, lower body movements will be permitted, however, participants will be encouraged to keep their feet flat on the ground, with their legs uncrossed. During the *Active Breaks* trial, participants will interrupt their 7-hours of sitting every 30 minutes with 3-minute bouts of self-paced, light-intensity walking. The first walking bout will be timed to occur 30 minutes following participants are first seated. Water will be provided *ad libitum* throughout each trial and participants will be encouraged to take bathroom breaks that coincide with their lunch break. During bathroom breaks, a wheelchair will be used to transport participants to the nearest distance to the bathroom from any of the sites (~10m). This will be measured from the seated position to the door of the bathroom.

Following 3.5 hours, lunch will be provided. Participants in the *Active Breaks* group will be instructed to complete their 3-minute walk prior to food consumption. Each participant will be instructed to consume their meal within 20 minutes. On completion of the 7-hour trial, participants will be instructed to lay supine to begin the post-testing measures. After ~60 minutes participants will then leave the lab.

#### Post-experimental procedures

Participants will be given instructions to continue wearing their activPAL physical activity monitor in order to record physical activity, in addition to recording their diet via MyFitnessPal for 48 hours following the trial. At least 4 days will separate the two trials to avoid wash-over effects.

Participants will receive a £50 Love2Shop voucher after completion of the study (final visit on the final day).

#### 6. Project setting

The study will be conducted across multiple study sites: School of Sport, Exercise and Rehabilitation Sciences (SportExR) at the University of Birmingham (UoB), School of Sport and Exercise Sciences at Liverpool John Moores University (LJMU) and Department of Sport and Exercise Sciences at Manchester Metropolitan University (MMU). All data collection will take place across these sites by a member of the research team.

#### 7. Participant recruitment

#### 7.1. Eligibility criteria

#### 7.1.1. Inclusion criteria

- Having been diagnosed with T1D for more than 3 years
- Aged 18-66 years
- Not currently meeting physical activity guidelines of > 150 min/week of moderate-intensity exercise or >75 min/week of high-intensity exercise
- being sedentary (inactive) form more than 8h per waking day (sitting or lying)
- Spending <5h per day seated or sedentary

- Currently using hybrid closed-loop insulin delivery system

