# Project summary

Study Title	The effect of interrupting sitting with regular active breaks on peripheral and cerebral blood flow in adults with type 1 diabetes			
Internal ref. no. / short title	Sitting and vascular health in people with T1D (ERN no: 2934)			
Proposed start date	01/02/2025			
Proposed end date	01/08/2026			
Countries in which the study will take place	England			
Study Design	Randomised crossover trial			
Study Participants	Habitually sedentary people type 1 diabetes using a closed-loop insulin delivery system			
Planned Sample Size	24			
Planned Study Period	18 months			
	Objectives	Outcome Measures		
Primary	To determine the effect of active breaks on change in superficial femoral artery flow-mediated dilation (FMD) compared to 7 hours compared to uninterrupted sitting.			
Secondary	To determine the effect active breaks compared to 7 hours of uninterrupted sitting on markers of glycaemia as assessed by continuous glucose monitoring (CGM). Glucose data gathered from closed-loop systems will be split into three time blocks; 1). 48 hours prior to the experimental period; 2). Experimental period (~7 hours); 3). 48 hours post-experimental period.	a) mean glucose b) % of time in level 2 hypoglycaemia (<3.0mmol/L) c) % of time in level 1 hypoglycaemia (3.0-3.9mmol/L) d) % of time in level 1 hyperglycaemia (10.0- 13.9mmol/L) e) % of time in level 2 hyperglycaemia (>13.9mmol/L) f) glycaemic variability, reported as CV and SD g) episodes of hypoglycaemia and hyperglycaemia h) area under the curve of episodes of hypoglycaemia and hyperglycaemia.		
	To determine the effect of active breaks on insulin dose compared to 7 hours compared to uninterrupted sitting.			

To determine the effect of active breaks on cerebrovascular function compared to 7 hours of uninterrupted sitting.	Middle cerebral artery velocity (MCAv)
To determine the effect of active breaks on markers of inflammation	
 
Endothelin-1 (ET-1) concentrations
 
Vascular cellular adhesion molecule concentrations (VCAM-1)
 

	
 
3) Intracellular adhesion molecule (ICAM-1)
 
4) Interleukin 6 (IL-6) concentrations
 

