#### 7.2. Sampling

#### 7.2.1. Size of sample

Twenty-four adults with T1D will be recruited

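### Two inclusion criteria on sedentary time exclude each other (more than 8 h and less than 5 h a day), so nobody is eligible as written

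*Protocol*

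**What the plan says.** Section 7.1.1 of the protocol gives the inclusion criteria as a single bulleted list. Two neighbouring bullets set limits on sedentary time:

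- "being sedentary (inactive) form more than 8h per waking day (sitting or lying" (closing bracket omitted here)
- "Spending <5h per day seated or sedentary"

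The list has no *or*, no subgroup and no separate time window that would make these alternatives. The second bullet does not define sedentary differently from the first.

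The Project summary describes the participants as "Habitually sedentary people type 1 diabetes using a closed-loop insulin delivery system". Section 7.1.1 also requires them to be "Not currently meeting physical activity guidelines of > 150 min/week of moderate-intensity exercise or >75 min/week of high-intensity exercise", and section 7.1.2 excludes people who take structured exercise. No other section gives a threshold for daily sedentary time.

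**The concern.** Inclusion criteria apply jointly: a candidate must meet all of them. One criterion here sets a floor of 8 hours on sedentary time and the next sets a ceiling of 5 hours on what appears to be the same quantity. A floor above a ceiling leaves nobody eligible.

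Two things are at stake. The first is compliance. Any enrolment would depart from the approved criteria, and section 10.5 says that frequently recurring deviations are unacceptable and may be classed as a serious breach. The second is who is studied. Whoever screens has to set one bullet aside, and the choice decides the population. People who sit for less than 5 hours a day are not the habitually sedentary group the trial sets out to study. With three sites (section 6), the text does nothing to ensure that all set aside the same bullet.

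**Working it through.** The protocol gives no figure to reproduce here, and no power or error-rate formula applies. The check is a logical one.

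**Inputs**

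| Item | Value | Source |
|---|---|---|
| Criterion A, sedentary time in the waking day | more than 8 h | Section 7.1.1 |
| Criterion B, seated or sedentary time in the day | less than 5 h | Section 7.1.1 |
| Target population | habitually sedentary | Project summary |
| Planned enrolment | 24 | Section 7.2.1 |
| Length of the sitting condition | 7 h | Section 5 |

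**Step 1. Put both criteria on one scale.** Let W be the sedentary hours in the waking day and D the sedentary hours in the whole day. Waking hours are part of the day, so D ≥ W.

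**Step 2. Combine them.** Criterion A requires W > 8, hence D > 8. Criterion B requires D < 5. No value of D satisfies both, and the limits lie 8 − 5 = 3 h apart. Whether sedentary time is counted over waking hours or over 24 hours makes no difference, because counting more hours can only raise D.

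**Step 3. Apply this to the planned sample.** The protocol states "Twenty-four adults with T1D will be recruited". The eligible share of any candidate pool is 0%, so all 24 enrolments would breach A, B or both.

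**Step 4. Ask which criterion fits the rest of the document.** The Project summary, the activity limit in section 7.1.1 and the exclusion of structured exercise in section 7.1.2 all describe inactive people. They agree in direction with A and not with B. For someone who meets B, the 7 hours of sitting in the Sedentary condition would exceed the usual total for a whole day by more than 7 − 5 = 2 h.

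**Step 5. Look for a rule elsewhere that settles it.** Under section 5, the research team assesses eligibility on a video call. The items listed for the online questionnaire that follows consent do not include sitting time. The activity questionnaire is completed at the laboratory visit, and the activity monitor is worn for the 48 hours before the first trial. Neither is described as a screening tool. Section 7.1.1 is therefore the only stated rule on sedentary time.

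**The case against.** The strongest reply is that this is an evident slip with little practical effect. Every other indication points to an inactive population, section 10.5 provides for weekly local and monthly all-investigator meetings, and a site recruiting the opposite kind of person would probably be noticed. The likely outcome is that staff ignore the 5-hour bullet. Each participant also receives both conditions, so the wording does not in itself bias the comparison of flow-mediated dilation. All of this is fair. Divergence between sites is a possibility that the text fails to prevent; nothing shows that it will happen.

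The inequality sign may also have been misread when the PDF was converted to text, since the converted line ends in a stray formatting tag. This should be checked against the source. But the tag stands at the end of the line, away from the sign, and the less-than sign reads sensibly in section 7.1.2. If the source had a greater-than sign, the bullet would be redundant, because anyone above 8 h is also above 5 h. That would be an editorial fault only.

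A third reading would admit someone who is seated for less than 5 hours but lies awake long enough to pass 8. It fails because the first bullet counts lying as sedentary and the second limits seated or sedentary time.

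Finally, the document does not say how the bullet arose. It could be surplus text, a reversed sign, or an exclusion criterion placed in the wrong list. That uncertainty stands, but removing the bullet from the inclusion list clears the conflict in all three cases.

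**Conclusion.** The concern holds. As written, the two criteria cannot both be met: 0% of candidates qualify, and all 24 planned enrolments would breach at least one inclusion criterion. This rests on reading the bullets as jointly required, which is how the list presents them, and on the less-than sign being as it appears in the text.

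The fault concerns eligibility and the definition of the study population. No effect on power, error rate or the treatment contrast is claimed. It must still be corrected, because the enrolment rule cannot be followed in its present form and nothing else in the protocol replaces it.

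**What to change.** Delete the 5-hour bullet from section 7.1.1 and keep one sedentary-time criterion that matches the habitually sedentary population in the Project summary. If the bullet was meant as an exclusion, the retained criterion already covers it: a person below 5 h cannot exceed 8 h. State whether the threshold refers to waking hours, and apply the same threshold in the screening call and the questionnaire at all three sites.

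The cost is a one-line protocol amendment and a matching change to the screening form. No extra participants or procedures are needed. Anyone already enrolled should be checked against the corrected criterion.

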#### 7.1.2. Exclusion criteria

- Under 18 years of age
- Engaging in structured planned exercise (e.g. running, cycling, gym, or sports)
- Pregnant or planning to become pregnant
- <6 months postpartum or stopped breastfeeding <1 month before recruitment
- Having been diagnosed with cerebrovascular or cardiovascular disease
- Having a significant history of uncontrolled hyperglycaemia (HbA1c >85 mmol/mol)
- Having a history of severe hypoglycaemia requiring third party assistance within the last 3 months
- Illness within the last 2 weeks

#### 7.2. Sampling

#### 7.2.1. Size of sample

Twenty-four adults with T1D will be recruited

#### 7.2.2. Sampling technique

Sampling techniques will include a combination of convenience, snowball and purposive sampling. We will use these sampling techniques due to the specific nature of the inclusion criteria of the study and the required sample size.

#### 7.3. Recruitment

Recruitment will take place via several methods. Once a suitable participant has expressed an interest in the study a participant information sheet will be sent to them, and a short initial meeting will be arranged (approx. 30 minutes). Meetings will be via telephone or video link depending on the participants preference. Following assessment of eligibility, the study will be explained detailing no less than: the exact nature of the study; what it will involve for the participant; the implications and constraints of the protocol; the known side effects and any risks involved in taking part. It will be clearly stated that the participant is free to withdraw from the study at any time for any reason without prejudice to future care, without affecting their legal rights, and with no obligation to give the reason for withdrawal. Participants will also be able to ask any questions they may have.

#### 7.3.1. Sample identification

Participants will be sampled through a combination of convenience and snowball sampling, with targeted recruitment based on the relevant inclusion/exclusion criteria of the study via the following methods.

- 1. Clinical database searches, and subsequent recruitment letters and text messages/SMS from participating diabetes clinics (Queen Elizabeth Hospital, Birmingham) searches will be for patients currently using closed-loop insulin delivery systems
- 2. Emails sent to volunteers within the 'research for the future' consent to approach database
- 3. Advertisement on the Diabetes UK website through the "take part in research" portal
- 4. Advertisement on the JDRF UK website through the "opportunities to take part in research" page
- 5. Advertisement through diabetes support groups
- 6. Advertisement on social media (e.g. Twitter (X) and Facebook)
- 7. Advertisements in newspapers
- 8. Advertisement to businesses through their occupational health team or other appropriate department
- 9. University of Birmingham and LJMU staff and students: via advertisements around the campus and via internal emails.
- 10. Posters displayed in high traffic areas within the health care system, diabetes websites and social media

Interested participants will contact the research team via email and be provided with a participant information sheet, unless otherwise stated.

# 7.3.2. Consent

Following the initial meeting participants will be asked to provide informed consent. If participants wish to take longer to decide this will be possible and no time limit will be placed on this. During this time, participants will be free to question the investigator, their GP or other independent parties to decide whether they wish to participate in the study. The participant will also have a hard copy of the participant information sheet. Patients will sign the Informed Consent document using the eSignature solution(HELLO SIGN), in line with HRA advice (Sept 2018). A copy of the signed Informed Consent will be given to the participant. The original signed form will be retained at the study site.

#### 8. Storage and analysis of human tissue

Blood samples will be stored in freezers located in a card-only access areas within UoB, LJMU and MMU. All samples will be stored in vials labelled by sample and participant ID number that can only be identified by

members of the investigative team. All samples will be stored, accessed, and processed in accordance with national legislation relating to the use and storage of human tissue for research purposes and such activities will meet the requirements as set out in the 2004 Human Tissue Act. Samples remaining at the end of the study will be destroyed in accordance with the 2004 Human Tissue Act.

### 9. Safety reporting

Patients will be asked if an adverse event (AE) (see below for definition) has occurred during meetings held post intervention. Should an AE be reported the study's lead clinician [name] will assess the event and the end outcome using the Serious Adverse Events Report Form. The PI will then report the event to the sponsor using the SAE Letter Template.

Serious adverse events are defined as any adverse event at any stage in the research participation of the study which:

- results in death
- is life threatening
- requires hospitalisation or prolongation of existing hospitalisation
- results in persistent or significant disability or incapacity
- is a congenital anomaly/ birth defect

Life-threatening refers to an event in which the participant was at risk of death at the time of event; it does not refer to an event which hypothetically might have caused death if it were more severe.

Expected adverse events include:

- Hypoglycaemia that could deal with by self
- Hyperglycaemia that could deal with by self
- Cough and Colds
- Flu
- Muscle aches and pains
- Muscle strains
- Indigestion
- Constipation
- COVID-19

## 10. Ethical and regulatory considerations

The Investigator will ensure that this study is conducted in accordance with the principles of the Declaration of Helsinki and relevant regulations.

#### 10.1. Assessment and management of risk

Risk of hypoglycaemia: To minimise the risk of hypoglycaemia resulting from an unfamiliar diet, participants will be provided with the macronutrient content of the food so participants can determine the correct dose of insulin. On the day of testing, the participants will be provided with a standardised breakfast, with a calorie content that is matched to their habitual diet. Should participants experience hypoglycaemia during the vascular measurements, they will be treated using a standard protocol. Participants will be provided with 15g of carbohydrates (Skittles). Blood glucose will be reassessed after 10 minutes. Should blood glucose still be <4.0 mmol/l another 15g portion of carbohydrates will be provided. The process will be repeated until blood glucose returns above 4.0 mmol/l. This is a standard procedure within our lab and others. For the rest of the

experimental period participants will be able to control blood sugar as they feel necessary. People with type 1 diabetes are experienced at monitoring their own blood glucose and appropriate actions to take. Finally, the research team also have great experience of running similar projects in people with type 1 diabetes

Ultrasound gel – allergic reaction: Participants will be asked if they have any known allergy to the gel. If so, the participants will not be tested for this measure. However, we do not envisage this to be an issue.

The researcher conducting the tests will monitor the participant for any possible allergic reaction throughout the test, if any signs of an allergic reaction occur then the testing protocol will be stopped and the participant will be referred to their GP.

Prolonged sitting – can lead to deep vein thrombosis (DVT) and pressure sore: Participants will be permitted to move their arms and legs freely and adjust their body position within their chair. This will maintain blood flow and reduce the risk of blood pooling. In addition, participants will be free to get up and move if in pain or discomfort. This will not affect their participation in the study or reimbursement. The participant will be free to stop the testing immediately and withdraw from the study at any time throughout the testing protocol.

Discomfort caused by the occlusion cuff: The participant will be warned before the test commences about the sensation that is caused during this test. The researcher will ensure that the cuff is fitted correctly, and the pressure is set correctly (220 mmHg). The participant will be free to stop the test at any time if they wish. The occlusion cuff will be released and removed; the test will not be continued. The participant will be free to withdraw from the study at any time.

Discomfort caused by the blood sampling needle: The participant will be warned before the test commences about the sensation that is caused during this procedure. The researchers taking the blood samples will be trained in venepuncture.

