### 5. Design and methods of data collection and data analysis

**Study design:** The study will use a randomised, crossover design, in which the same participants will complete two 7-hour experimental trials. One condition will involve participants sitting uninterrupted for 7-hours (*Sedentary*), while the other condition will require participants to interrupt 7-hours of sitting with 3-minutes of light-intensity walking every 30 minutes (*Active Breaks*). During both conditions, blood flow (peripheral and cerebral), arterial diameter and blood markers will be measured on two separate occasions (baseline and post (7hrs)). Interstitial glucose levels and insulin administrated by the hybrid closed loop will be recorded 7 days prior to, during and 7 days following each trial visit. Diet and physical activity for each participant will be controlled for 24-hours prior to and during and for the evening following each visit each trial visit.

The study will use a randomised, counterbalanced, crossover design, whereby participants will complete two experimental periods, each period will include a laboratory visit where the effects of 7 hours exposure to one of either 2 conditions will be investigated:

- A. Continuous sitting (Sedentary)
- B. 3 minutes of light-intensity walking every 30 minutes (Active Breaks)

Lab visits will be identical except for the condition and will be separated by at least 4 days. Females will be tested in the early follicular phase of the menstrual cycle to control for hormonal fluctuations. Female participants will be provided with the option to opt-out of a question relating to the menstrual cycle during the questionnaire and are welcome to talk to a female member of the research team on request. If they do not wish to disclose this information, then they will be excluded from the study and will not complete any further procedures.

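### The protocol gives different rules for managing low glucose while participants sit: a fixed rule under Lab Visits, participant discretion under section 10.1

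*Protocol*

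**What the plan says.** Three places in the protocol deal with low glucose or extra food around the visit.

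- **Section 5, Lab Visits.** After the baseline measurements, "Once this is complete (~09:00), participants will then be supervised while they sit at a workstation". From then, "food intake will be restricted until lunch (3.5 hrs" after sitting starts). The exception is glucose below 4 mmol/L, when "participants will be provided with 15g of carbohydrates (Skittles). Blood glucose will be reassessed after 10-minutes", with further 15 g portions until glucose is above 4. The same section later adds: "Following 3.5 hours, lunch will be provided".
- **Section 10.1, risk of hypoglycaemia.** "Should participants experience hypoglycaemia during the vascular measurements, they will be treated using a standard protocol": the same 15 g portion and 10-minute recheck. For the rest of the "experimental period participants will be able to control blood sugar as they feel necessary".
- **Section 5, Standardisation of diet.** Apart from the supplied meals, including the one on the lab day, participants are asked not to eat unless they need to head off or correct hypoglycaemia. No preventive trigger and no amount is given.

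The study design text in section 5 states the intention: "Diet and physical activity for each participant will be controlled for 24-hours prior to and during" each visit. It also says that the two lab visits differ only in condition.

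**The concern.** For the seated hours, one section prescribes a fixed treatment given by staff, and another appears to hand glucose control to the participant. Staff at the three sites could each follow the protocol and still act differently.

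The seated hours matter because the Project summary and section 4.2 make an experimental period of about 7 hours one of three glucose analysis blocks. Mean glucose, time in the low and high ranges, variability and episodes in that block are secondary outcomes, and carbohydrate acts directly on all of them. The Randomisation and Blinding text accepts that participants cannot be blinded. Someone who walks every 30 minutes might eat to pre-empt a low, and the same person might not do so on the sedentary day. That would work against the stated diet control during the visit.

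An imbalance might also go unseen. The food diary is specified for 48 hours before and 48 hours after each trial, and the protocol text does not say that extra carbohydrate taken during the visit is recorded.

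**Working it through.** No statistical figure is involved, so the check sets the texts side by side along the visit timeline.

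**Timeline, from Lab Visits**
- Arrival: about 07:30. Questionnaires and supine baseline measurements run to about 09:00.
- Sitting starts: about 09:00.
- Lunch: 09:00 + 3.5 h = about 12:30.
- Sitting ends: 09:00 + 7 h = about 16:00. Supine post-measurements follow, for about 60 minutes.

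**When are the vascular measurements?** The design text says that "arterial diameter and blood markers will be measured on two separate occasions (baseline and post (7hrs"). None falls inside the seated block.

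**Which rule applies in each interval?**

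| Interval | Lab Visits | Section 10.1 | Standardisation of diet |
|---|---|---|---|
| Baseline measurements | no separate rule | 15 g scheme | food to prevent or correct a low |
| 09:00 to 12:30, seated | no food; 15 g scheme below 4 mmol/L | participant's discretion | food to prevent or correct a low |
| 12:30 to 16:00, seated | food restriction has lapsed; reach of the 15 g scheme not stated | participant's discretion | food to prevent or correct a low |
| Post-measurements | no separate rule | 15 g scheme | food to prevent or correct a low |

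The texts diverge most plainly between the start of sitting and lunch, which is 3.5 of the 7 seated hours. After lunch the divergence is arguable, because Lab Visits states its food restriction only up to lunch. The 3.5 h count from sitting down and not from arrival. The 1.5 h before sitting (07:30 to 09:00) include the baseline vascular measurements, where the two sections do not conflict.

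**Does the meaning of *experimental period* remove the problem?** The protocol uses the term in more than one sense.
1. In the Project summary and section 4.2 it is about 7 hours, separate from the 48-hour blocks on either side. The discretion in section 10.1 then falls on the lab day itself.
2. In the design text it is a wider period that contains a laboratory visit. The seated block is still inside that period and still outside the vascular measurements, so the discretion still reaches it.
3. It is also the heading over the pre-visit checks, which settles nothing.

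No sense of the term takes the seated hours out of the section 10.1 sentence, and no section says which rule prevails.

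**Size of effect.** This would need the frequency of lows, the amount of extra carbohydrate by condition and the variability of glucose. The protocol gives none of these, so no bias can be calculated. The hours above show where the rules differ, not how much harm follows.

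**The case against.** The best reply is that this is loose wording and not a contradiction. Lab Visits is the operating procedure, while section 10.1 is a general risk paragraph that repeats the same treatment. Its discretionary sentence mentions neither food nor carbohydrate and does not lift the food restriction. Every participant uses a hybrid closed-loop system, so controlling blood sugar could mean using that system, and no insulin rule is contradicted. The sentence that follows, on participants' experience in monitoring their own glucose, fits self-management at home. Supervision, supplied meals and the Standardisation of diet instruction already limit snacking on the lab day. Visits are also re-arranged if morning glucose is outside 4 to 10 mmol/L.

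Much of this stands. The intent may well have been a fixed rule in the lab and self-management elsewhere, and the carbohydrate conflict is a literal reading of a sentence that does not name carbohydrate. But section 10.1 does not say that its discretion stops at the lab door, and taking carbohydrate is an ordinary way to control blood sugar. The diet instruction limits extra food but permits preventive eating without a trigger or amount.

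A reader might go further and infer that the glucose comparison is biased in a known direction, or that the FMD result is compromised. The protocol supports neither. The wording is the same for both conditions, so a difference between them is a possibility and not a finding. Rescue carbohydrate can also differ by condition under the fixed rule if lows do.

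**Conclusion.** The inconsistency is real and minor. Read literally, section 10.1 allows discretionary glucose management, including carbohydrate, by unblinded participants during hours for which Lab Visits sets a fixed rule, and inside the window used for the glucose secondary outcomes. The size and direction of any effect are unknown, and no effect on FMD is shown. Insulin is involved only indirectly, since section 4 describes it as a total daily dose.

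The conclusion rests on two assumptions: that staff or participants might act on section 10.1 as written, and that controlling blood sugar includes taking carbohydrate. If all sites already follow Lab Visits throughout the visit, only the wording needs correcting. It would be wrong to infer an outright clash over the whole visit: the texts agree for the vascular measurements, and the conflict after lunch is arguable.

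**What to change.** - Amend section 10.1 so that the Lab Visits treatment rule (15 g below 4 mmol/L, recheck at 10 minutes, repeat until above 4) covers the whole lab visit: the measurement periods and the seated block before and after lunch, in both conditions and at all sites. Limit self-management to time outside the lab.
- For the lab visit, give the preventive carbohydrate allowed under Standardisation of diet one stated glucose trigger and amount, the same in both conditions. Do not ban it, because a ban would carry a safety cost.
- Record the time and amount of all extra carbohydrate taken in the visit and report it by condition. This is needed even under the fixed rule, because the number of treated lows may differ between conditions.

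The cost is a wording amendment, one extra line on the visit form and slightly less participant discretion in the lab.
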